Recruitment: Subjects will be recruited exclusively through the ARMS program at MGH. ARMS is an outpatient, dual diagnosis clinic comprising a multidisciplinary team of psychiatrists, clinical psychologists, and masters-level social workers who are trained to work with adolescents and young adults with substance-related problems. ARMS provides comprehensive outpatient individual therapy, group therapy, and outpatient psychiatry consultation and follow-up. The investigators have obtained commitment from the Clinical Director of ARMS ([name]) to support recruitment of young adult patients at ARMS, and to facilitate delivery of the group-based experimental intervention. The ARMS program conducts evaluations with approximately 180 new patients per year, the majority of whom also present with comorbid depression or anxiety. We will collaborate with the ARMS Clinical Director and staff in order to recruit through study flyers and direct referrals from the ARMS clinicians (psychiatrists, psychologists, social workers) who conduct routine clinical evaluations.

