measures of anxiety or depression used for clinical purposes at ARMS, and/or report of suicidal thoughts or NSSI in the past week) will be enrolled in the study. An ARMS clinician will determine possible subject eligibility based on information obtained during the routine clinical evaluation for ARMS treatment. Those who are deemed potentially eligible and express interest in the study will then undergo a brief in-person screening visit with a study clinician. The screening visit, which will take about 60 minutes, will consist of a meeting with a study clinician to provide informed consent and confirm study eligibility (via review of information obtained during routine ARMS clinical care and completion of the SITBI-CR). For participants who report suicidal thoughts in the past week or having made a suicide plan or suicide attempt in the past year on the SITBI-CR, a clinical risk assessment (including severity of ideation and presence of plan, intent, and access to means) will be conducted during the visit in order to ensure participant safety and eligibility for the study (i.e., no imminent suicide risk). The study clinician conducting the screening visit will consult the ARMS Clinical Director (or, if [name] is unavailable, another licensed clinician on-site) immediately regarding risk in any questionable cases to determine the appropriate action, per usual ARMS clinical procedures. Eligible participants will then complete the Timeline Follow Back (TLFB^{53,54}) as an interview, in which participants recall the quantity and frequency of substance use during a specified time window (e.g., past month) using a calendar, and several self-report questionnaires, including the BSI, CCS, and Craving Scale (see Table 1). The study clinician will also fill out a concomitant treatment log to identify the participant's overall treatment plan, including medication and therapy. Data obtained at this screening visit will be considered the "pre-treatment" assessment. After eligibility criteria are determined and participants have completed the screening/baseline assessment, participants will be randomly assigned to UP+TAU or TAU only conditions using a permuted block randomization procedure. The permuted block randomization schedules will be generated by an independent biostatistician from the MGH Biostatistics Center prior to enrolling the first subject into the study. Groups, or "blocks," of 5 individuals will be randomized at a time to one of the two treatment conditions (UP+TAU or TAU alone) using a 2:1 randomization scheme, defined as 2 blocks randomized to UP + TAU for every 1 block randomized to TAU alone. Randomizations will be conducted using a web-based randomization program developed by the MGH Biostatistics Center. The randomization code will be generated within the webbased program by study staff only when the randomization occurs, i.e. once the last participant of each group has completed baseline. Participants will then be contacted by study staff via their preferred method of communication to notify them of their study condition.

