TAU condition: After randomization, participants randomized to the TAU condition will undergo usual care at ARMS for the next 8-10 weeks. Usual care at ARMS typically consists of a combination of up to 3 group therapy sessions per week, individual weekly therapy, and/or psychopharmacology appointments as needed. Some ARMS patients are offered and choose to engage in all three treatment modalities (group therapy, individual therapy, and psychopharmacology), whereas others only engage in one treatment modality. No requirements will be placed on TAU participants with regard to TAU dosage and TAU will be consistent with each participant's clinical treatment plan at ARMS; however, TAU attendance (e.g., number of appointments) for all participants will be tracked by study staff. Four to 6 weeks after randomization, TAU participants will complete a mid-treatment assessment, during which they will complete the same self-report questionnaires (plus TLFB and concomitant treatment log with a study clinician) administered at the screening/baseline visit (see *Measures*). Eight to 10 weeks after randomization, they will repeat the same measures for the in-person "post-treatment" assessment. During both the mid- and post-treatment assessments, should a participant report suicidal thoughts in the past week on the SITBI-SR or clinically significant increases in NSSI, a clinical risk assessment (including severity of ideation and presence of plan, intent, and access to means) will be conducted by a study clinician in order to ensure participant safety and that the

participant remains stable to be treated in an outpatient setting. After completing the post-treatment assessment, their study participation will be complete.

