UP + TAU condition: After randomization, participants randomized to the UP + TAU condition will undergo TAU at ARMS and be offered 16 additional, twice-weekly group UP sessions, also at ARMS (see *Intervention*). Participants in the UP + TAU condition will undergo the same midand post-treatment assessments as the TAU condition, plus the CSQ-8 and a semi-structured interview to collect feedback about the intervention (see *Measures*). The mid-treatment assessment will occur after each participant's 8th UP session OR between 4-6 weeks after randomization, and the post-treatment assessment will occur within two weeks after each participant's 16th UP session. The same risk assessment procedures for mid- and post-treatment assessments used in the TAU condition will also apply to the UP + TAU condition. Should a UP + TAU participant condition have two consecutive unplanned absences from a UP group session, up to three attempts to contact will be made regarding their absence. There will not be a maximum number of missed UP sessions warranting a participant to step out of the 16-session group protocol. After completing the post-treatment assessment, their participation in the study will be complete.

Group UP sessions will take place at the ARMS program at MGH. Study assessment visits (screening/baseline, mid-treatment, and post-treatment) may take place at the ARMS program, the Depression Clinical and Research Program (DCRP), or the Center for Addiction Medicine (CAM) at MGH. Study staff may walk participants between ARMS and the DCRP or CAM as needed.

In sum, the proposed study involves the following points of contact: (1) obtaining informed consent and screening/baseline assessment, (2) mid-treatment assessment involving self-report questionnaires and TLFB, (3) post-treatment assessment involving self-report questionnaires and TLFB (primary endpoint), and (4) 16 twice-weekly group UP sessions for those randomized to the UP + TAU condition.

If participants are unable to complete the clinician-rated measures in-person at their mid- or post-treatment assessments, they will be given the option to complete this portion of the visit via phone call with a study clinician. Should any risk issues arise, the clinician will complete a risk assessment while on the phone with the participant. A licensed clinician will always be on-site for consultation as needed during assessments conducted over the phone.

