If participants are unable to complete the self-reported measures in-person at their screening/baseline, mid-treatment, or post-treatment assessments, they will be e-mailed a link to the self-report battery in Redcap to complete remotely. Study staff will review the completed SRQ assessment in Redcap within 24 (business) hours of submission for report of suicidal thoughts, and within one week to assure their completeness. Should a participant report suicidal thoughts in the past week on the SITBI-SR, a clinical risk assessment (including severity of ideation and presence of plan, intent, and access to means) will be conducted over the phone by a study clinician to ensure participant safety and that the participant remains stable to be treated in an outpatient setting. Additionally, a clinical risk assessment will be conducted over the phone by a study clinician in response to reports of increased NSSI that are deemed clinically

significant. Up to three attempts to contact will be made for this risk assessment before calling a participant's designated emergency contact.

Participants may receive recruitment and scheduling messages, as well as appointment reminders via e-mail or text message over the course of the study, depending on their preferred method of communication. Up to three consecutive (unanswered) contact attempts to the participant will be made for participants in both conditions to schedule mid- and post-treatment assessments. If a participant misses the mid-treatment assessment, but is still responsive to contact attempts, they will still be able to complete the post-treatment assessment. If a participant in either condition is unresponsive to three consecutive unanswered contact attempts within a three-week period at any point within the 10-week study, they will be considered dropped out from the study and no further follow-up will be made; the ARMS clinical team will also be notified.

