Emotion Regulation Questionnaire (ERQ⁵⁵). The ERQ is a 10-item self-report measure assessing two emotion regulation strategies—cognitive reappraisal and expressive suppression. It will be used at the three assessment points to capture changes in emotion regulation during the study.

Brief Experiential Avoidance Questionnaire (BEAQ⁵⁶): The 15-item BEAQ is a modified, briefer version of the original 62-item Multidimensional Experiential Avoidance Questionnaire (MEAQ), self-report measure of six experiential avoidance domains: behavioral avoidance, distress aversion, procrastination, distraction/suppression, repression/denial, and distress endurance. It will be used at the three assessment time points to capture changes in experiential avoidance.

Overall Anxiety Severity and Impairment Scale (OASIS⁵⁷). This is a 5-item, self-report measure assessing the anxiety-related severity and impairment in the past week. It will be administered at each of the three assessment points to participants in both conditions. Participants in the UP + TAU condition will also complete it at the start of each UP session, per the treatment protocol³⁷.

Overall Depression Severity and Impairment Scale (ODSIS⁵⁸). This 5-item, self-report measure captures severity and impairment of depression in the past week. It will be administered at each of the three assessment points to participants in both conditions. Participants in the UP + TAU condition will also complete it at the start of each UP session, per the treatment protocol³⁷.

Self-Injurious Thoughts and Behaviors Interview-Clinician-Rated Version (SITBI-CR⁵⁰). This clinician-rated measure will be used to capture suicidal thoughts and behaviors and NSSI over lifetime, past year, past month, and past week at the screening/baseline visit.

Self-Injurious Thoughts and Behaviors Interview-Self-Report Version (SITBI-SR⁵⁰). This self-report measure will be used to capture suicidal thoughts and behaviors and NSSI in the past month at the mid-treatment and post-treatment assessments.

Timeline Follow Back (TLFB^{53,54}). The TLFB will be administered as an interview at all three time points in order to determine frequency and quantity of substance use, as well as percent days abstinent, since the last assessment (or at pre-treatment, over the past month). For the TLFB, participants mark the days on which they used a substance and indicate which substance(s) (and how much) they used.

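### The TLFB look-back makes the mid-treatment substance-use value include days before the delayed group randomization, which dilutes that time point

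*Protocol*

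**What the plan says.** The TLFB entry in the protocol's list of measures (Section V) says that the interview yields frequency and quantity of use, and percent days abstinent (PDA), "since the last assessment (or at pre-treatment, over the past month". Participants mark individual days of use on a calendar.

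Section IV fixes what precedes the mid-treatment visit: "Data obtained at this screening visit will be considered the" pre-treatment assessment. It also fixes when randomization happens. Groups of five are allocated together, "i.e. once the last participant of each group has completed baseline".

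Section V times the later visits differently. "Four to 6 weeks after randomization, TAU participants will complete a mid-treatment assessment". In UP + TAU, mid-treatment follows the 8th UP session or falls 4 to 6 weeks after randomization, "and the post-treatment assessment will occur within two weeks after each" participant's 16th session. The summary of contacts lists the "post-treatment assessment involving self-report questionnaires and TLFB (primary endpoint"). A missed visit is allowed for: "If a participant misses the mid-treatment assessment, but is still responsive to contact attempts", post-treatment can still be completed.

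Section VI analyses quantity, frequency and PDA by mixed models with a time-by-condition interaction. Hypothesis 2e concerns use during the study period, which is not defined.

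**The concern.** The look-back starts at the baseline visit, while the mid-treatment visit is mainly timed from randomization. Nothing in the protocol restarts the window at randomization or limits how long a group may take to fill. Allocation cannot affect use on days before it was made, so those days pull a per-day contrast at mid-treatment toward zero.

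Mid-treatment is one of three time points in the time-by-condition model. A diluted value there also carries weight when post-treatment is missing, because a likelihood-based model then leans on the observed mid-treatment value. Sections V and VI let the problem reach post-treatment directly when mid-treatment is skipped, since the previous assessment is then baseline. Section VI gives effect-size estimation as a primary purpose of the pilot, so an avoidable dilution is worth removing.

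**Working it through.** The protocol states no figure for this point, so there is none to reproduce. The check is timeline arithmetic.

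**Inputs from the protocol.** N = 50; groups of 5; mid-treatment 4 to 6 weeks (day 28 to 42) after randomization; about 180 new clinic evaluations per year (Section III, Recruitment: "The ARMS program conducts evaluations with approximately 180 new patients per year").

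**Assumption.** Trial accrual is not given. I take a steady rate of *a* participants per month (30.44 days). The value *a* = 180/12 = 15 means that enrolment equals every new evaluation. It is a reference case and not a ceiling, since existing patients may also enrol. The rates 6, 4 and 2 per month are assumed.

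**Who is affected.** 50/5 = 10 groups. In each, up to 4 members finish baseline before the last one: 10 × 4 = 40 of 50.

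**Wait before randomization.** Member *j* waits *w* = (5 − *j*)/*a* months.
- *a* = 15: 8.1, 6.1, 4.1, 2.0, 0 days (mean 4.1)
- *a* = 6: 20.3, 15.2, 10.1, 5.1, 0 days (mean 10.1)
- *a* = 4: 30.4, 22.8, 15.2, 7.6, 0 days (mean 15.2)
- *a* = 2: 60.9, 45.7, 30.4, 15.2, 0 days (mean 30.4)

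**Pre-randomization share of the window.** For a visit on day *d* after randomization, share = *w*/(*w* + *d*). Example, first member, *a* = 6, *d* = 28: 20.3/(20.3 + 28) = 42%. Averaged over the five members:

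| Window ends on day | 15/month | 6/month | 4/month | 2/month |
|---|---|---|---|---|
| 28 (mid) | 12.0% | 23.8% | 30.7% | 43.6% |
| 42 (mid) | 8.5% | 17.9% | 23.8% | 36.0% |
| 56 (late UP + TAU mid, or post with mid missed) | 6.5% | 14.3% | 19.5% | 30.7% |
| 70 (post with mid missed) | 5.3% | 12.0% | 16.5% | 26.8% |

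Random (Poisson) arrivals give similar values: 11.4, 22.1, 28.2 and 39.5% at day 28, and 8.2, 16.8, 22.1 and 32.8% at day 42.

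**Why day 56 is also a mid-treatment case.** A UP + TAU group randomized during UP Weeks 6-8 may wait up to 4 weeks to start. Eight sessions at two per week take another 4 weeks, so the 8th session can fall at about 4 + 4 = 8 weeks, day 56.

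**Effect on the contrast.** If the effect on the daily rate is a constant δ from randomization, the mid-treatment contrast is δ × *d*/(*w* + *d*) = δ × (1 − share). Under that assumption the proportional loss equals the share.

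**Post-treatment.** If mid-treatment was attended, the post-treatment window starts at mid-treatment and the share is 0%. If 10 to 30% of participants missed mid-treatment (an assumption) and post-treatment falls at day 70 to 56, the arm-level loss runs from 0.1 × 5.3% = 0.5% to 0.3 × 30.7% = 9.2%.

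**The case against.** The strongest reply is that the look-back is a collection rule, and a sound one: it keeps the calendar unbroken. Which days enter the analysed variable could be settled in a statistical analysis plan that is not shown. This stands in part. The interview need not change, and an analysis plan could trim the window. But the protocol names quantity, frequency and PDA as determined over this window, so it states a rule that yields a diluted value; it does not merely leave a detail open.

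A second reply is that little planned inference depends on mid-treatment. This stands. No section plans a stand-alone mid-treatment effect, so a reader who infers that the pilot will report one that is too small goes beyond the text. With complete data and an equally spaced linear time effect (weeks 0, 4, 8), the slope weights are −4/32, 0 and 4/32, so mid-treatment has no weight at all.

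A third reply is that the size is assumed. This also stands. Only the 8-12% case uses a flow figure from the protocol, and that figure is clinic intake, not trial accrual. The day 28-42 range does not cover every UP + TAU visit, and a constant effect from randomization is doubtful when UP itself may start weeks later. The part of any shortfall due to that later start belongs in an intention-to-treat comparison and is no defect.

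**Conclusion.** The point holds and merits correction, with a limited reach. The stated look-back puts pre-randomization days into the mid-treatment value for up to 40 of 50 participants, and into the post-treatment value for those who missed mid-treatment. The mean share of the mid-treatment window is about 8-12% if enrolment equalled all new evaluations, and about 18-44% at assumed rates of 6 to 2 per month with mid-treatment at day 42 to 28. For a UP + TAU visit near day 56 it is about 6-31% over the whole range of rates. The loss of effect equals the share only under a constant daily effect from randomization.

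Three stronger readings are not supported:
- **The design favours UP.** The wait ends before the group is allocated, so no arm is systematically favoured.
- **The primary endpoint is contaminated.** The post-treatment value contains no pre-randomization days when mid-treatment was attended.
- **Hypothesis 2e necessarily includes these days.** That follows only if the study period is counted from baseline. The period is undefined, and the drop-out rule's mention of a 10-week study fits a start at randomization.

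**What to change.** Keep the interview as it is. In both arms, define each post-baseline TLFB analysis window to start at the later of the randomization date and the previous completed assessment, and cut it from the daily calendar already collected. Record the randomization date with the TLFB data so that the cut can be made. State that the study period in Hypothesis 2e is counted from randomization. Keep all post-randomization days, including any wait for the UP group to begin, so that the comparison stays intention-to-treat.

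The pre-randomization share then becomes 0% for everyone. The cost is slightly more derivation work and somewhat less precise mid-treatment values for members who joined their group early, because their windows become shorter. No new data are needed and no post-randomization day is lost.
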